19.1 Clinical Classification of Patients based on PS Volume

On the basis of the energy and volume of the required PS, the patients are categorized into 16 combinations (adapted from Pironi *et al* (2016)⁸):

IV Energy Supplementation ^b (kcal/kg body weight)	Volume of IV Supplementation ^a (L)			
	≤ 1 [1]	>1-2 [2]	>2-3 [3]	> 3 [4]
0 (A)	A1	A2	A3	A4
1-10 (B)	B1	B2	B3	B4
11-20 (C)	C1	C2	C3	C4
> 20 (D)	D1	D2	D3	D4

IV=intravenous

a Calculated as daily mean of the total volume infused per week = (volume per day of infusion × number of infusions per week)/7.

b Calculated as daily mean of the total energy infused per week = (energy per day of infusion × number of infusions per week)/7/kg.

1. PURPOSE

The purpose of this statistical analysis plan (SAP) is to ensure that the summary tables, patient data listings, and figures which will be produced, and the statistical methodologies that will be used, are complete and appropriate to allow valid conclusions regarding the trial objectives.

This SAP is based on protocol ZP1848-17111, Version 10.0, dated 27 January 2022.

1.1. RESPONSIBILITIES

Zealand Pharma will perform the statistical analyses and is responsible for the production and quality control of all tables, listings, and figures.

2. TRIAL OBJECTIVES

2.1. PRIMARY OBJECTIVE

• To confirm the efficacy of glepaglutide in reducing parenteral support (PS) volume in SBS patients

2.2. SECONDARY OBJECTIVES

- To evaluate the efficacy of glepaglutide on other efficacy endpoints in patients with SBS
- To evaluate the safety and tolerability of glepaglutide in patients with SBS

2.3. ESTIMAND

Translating the primary trial objective into a precise description of the treatment effect to be estimated, leads to four components that together define the primary estimand of primary efficacy endpoint:

- 1. The population is defined as patients with SBS randomized into the trial and having received treatment
- 2. The endpoint is the change from baseline in actual weekly PS volume after 24 weeks
- 3. The effect of twice weekly and once weekly glepaglutide 10 mg, regardless of discontinuing treatment or not, is of interest
- 4. The summary measure is the difference in endpoint means between active (twice weekly and once weekly glepaglutide 10 mg) and placebo

Primary estimand of primary efficacy endpoint

• Difference between mean change from baseline in actual weekly PS volume at 24 weeks in the SBS population regardless of whether treatment is discontinued.

The estimand is constructed based on the 'treatment policy strategy' (ICH E9 (R1) addendum).

It is required to collect data after treatment discontinuation to get a reliable estimate of this estimand.

Furthermore, a supplementary estimand of primary efficacy endpoint is defined where the intercurrent event of discontinuing treatment is handled under a 'hypothetical strategy'. This corresponds to the following estimand of interest

• Difference between mean change from baseline in actual weekly PS volume at 24 weeks in the SBS population, as if treatment discontinuation never occurred.

2.4. STUDY POPULATION

The study population will consist of SBS patients with a stable need for PS at least 3 days per week. The exclusion criteria will ensure that randomized patients are not put at any undue risk and that there

are no concomitant diseases, conditions, or treatments that potentially could interfere with the interpretation of the data and results.

2.5. TRIAL DESCRIPTION

This is a multicenter, placebo-controlled, randomized, parallel-group, double-blind, fixed dose, Phase 3 trial to demonstrate the superiority of once weekly or twice weekly subcutaneous (SC) injections of 10 mg glepaglutide versus placebo in stable SBS patients.

After providing informed consent and initial confirmation of eligibility during the 2-week Screening period, patients will enter a PS Optimization and Stabilization Phase before baseline measurements are performed. An individual drinking menu will be defined by the patient and the Investigator during the Screening period and until the end of the Optimization Phase. Unless otherwise specified, baseline is defined as Day 1, prior to first dosing of trial product.

Optimization Phase

During the Optimization Phase, the Investigator may change the PS volume and content if the patient is considered unstable or not optimized. Any changes in PS volume or content will be administered according to institutional standard practice. The effect of any PS optimizations must be investigated after 2 weeks. Prior to an Optimization Phase visit, the patient must measure his/her urine over 48 hours, while adhering to the pre-defined drinking menu, and report the urine output in the eDiary. PS volume optimization consist of 2 rounds, which limits the Optimization Phase to a maximum duration of 4 weeks (\pm 4 days).). If optimization cannot be shown during the 4-week period, a second Optimization Phase of up to 4 weeks (\pm 4 days) is allowed. The last Optimization Phase visit can be combined with the first visit in the Stabilization period if the patient is considered stable.

Stabilization Phase

The Stabilization Phase has a minimum duration of 2 weeks and a maximum duration of 4 weeks (\pm 4 days). The last visit of the Optimization Phase can also be the first visit of the Stabilization Phase. Patients will be evaluated every 2 weeks during the Stabilization Phase and will need to fulfill the pre-specified stability criteria before the patient can be randomized. If stability cannot be shown during the 4-week period due to unforeseen events such as infections, illness or similar, a second Stabilization Phase of up to 4 weeks (\pm 4 days) is allowed.

A patient will be considered stable if all the following criteria are met:

- Actual PS usage (volume and content) matches prescribed PS (\pm 10% deviation in volume is acceptable) and
- 48-hour urine output volumes at 2 consecutive visits within a 2-week interval (\pm 4 days, i.e., visits should be 10 to 18 days apart) are similar (a maximum of \pm 25% deviation is acceptable), while the oral fluid intake is constant (the two 48-hour oral intakes differ less than 10%) and maximum 3.5 L per day and
- Urine output volume is on average ≥ 1 L and ≤ 2.5 L per day.

The Investigator and Medical Monitor must both agree and approve that the patient has met the criteria to be considered stable after completing the Stabilization Phase.

Main Trial Period:

All eligible patients who complete the Optimization and Stabilization Phases will be randomized in a 1:1:1 manner to receive either: a) glepaglutide 10 mg twice weekly, b) glepaglutide 10 mg once weekly and placebo once weekly, or c) placebo twice weekly SC for the following 24 weeks.

During the 24-week Treatment Phase, PS need will be evaluated by 48-hour balance periods involving urine measurements and during which patients will be required to keep to an individually pre-defined drinking menu (timing, volume, and content) and document this in the eDiary.

The actual volume of PS will be recorded daily in electronic diaries (eDiaries) by the patients. The Investigator will record the type, content, and volume of the PS being used. Once trial drug treatment is initiated, PS volume can be adjusted at trial visits (at Weeks 1, 2, 4, 8, 12, 16, 20, and 24) if the criteria for adjustment are met and according to a predefined algorithm.

Algorithm for PS volume reduction:

IF: daily urine volume of the current visit is at least 10% higher than baseline urine volume.

THEN: New PS volume (weekly) = Current PS volume (weekly) -7 x absolute increase in daily urine volume from baseline

The Investigator may arrange unscheduled visits (preceded by a 48-hour balance period) if he or she considers the visits to be needed based on medical judgement to assess PS volume needs.

It is acknowledged that intake of oral liquids and PS might have to be changed between scheduled visits to avoid edema, especially if treatment is effective. In such cases changes to the PS is at the discretion of the Investigator.

Any changes to the content of PS are left to the discretion of the Investigator.

After completing the Treatment Phase (regardless of treatment adherence), patients (patients in all 3 treatment groups) will be eligible to enter an Extension Trial and receive glepaglutide. For patients not entering the Extension Trial, a Follow-up Visit will be conducted 4 weeks after completion of the Treatment Phase.

2.6. DETERMINATION OF SAMPLE SIZE

The sample size calculation for this trial is based on the effect achieved in the teduglutide Phase 3 trial and that the PS volume changes from baseline after 24 weeks of treatment (primary endpoint) are expected to be -4.5 L/week and -4.3 L/week with twice-weekly and once-weekly dosing, respectively, and -2.3 L/week for placebo. The standard deviation of the treatment effect (once-weekly or twice-weekly versus placebo) is assumed to be 2.62. A total of 101-112 SBS patients are planned for inclusion, with 33-37 patients planned for each of the three treatment groups. The trial size will result in 93-95% power for detecting the assumed difference with either once-weekly or twice-weekly for the primary endpoint. The assumed effects include imputed effects for patients with missing data. The power calculations are shown in Table 1 including the scenario where once-weekly and twice-weekly dosing are assumed to be slightly worse.

Table 1 Power considerations

Power (%) to show superiority of either once-weekly or twice-weekly compared to placebo with respect to the
primary endpoint

Assumptions:			Number of patie	ents (total)		
PS vol, change from baseline (L/week)						
Twice-weekly One-weekly Placebo		99	108	117	129	
-4.5	-4.3	-2.3	93	95	96	98
-4.3	-4.1	-2.3	88	91	93	95

The two comparisons, once-weekly vs placebo and twice-weekly vs placebo are tested two-sided in parallel at α =0.025 to control the overall type 1 error at 5% level.

2.7. TREATMENT ASSIGNMENT & BLINDING

Randomization will be used to avoid bias in the assignment of patients to double-blind treatment (glepaglutide twice weekly, glepaglutide once weekly, or placebo) and to increase the likelihood that known and unknown patient characteristics will be evenly distributed between the treatment groups.

For each cohort, eligible patients will be randomly assigned on Day 1 after all visit procedures have been performed and eligibility for randomization confirmed. Patients will be randomized via an interactive web response system (IWRS) to receive trial drug (glepaglutide twice weekly, glepaglutide once weekly, or placebo) in a 1:1:1 ratio. Trial drug assigned to a patient may not be reused, even if the vial returned is unopened.

A designated randomization administrator from an external, independent vendor will maintain the randomization codes in accordance with standard operating procedures to ensure that the blind is properly maintained and only sponsor, CRO, and vendor personnel who require knowledge of treatment assignments will be unblinded during the trial.

Investigators are not to break the trial treatment blind except when information concerning the trial drug is necessary for the medical treatment of the patient. If a medical emergency requiring unblinding occurs, the investigator (or designated physician) is strongly encouraged to contact the medical or safety monitor to assess the necessity of breaking the trial drug blind. If unblinding is warranted, the investigator will obtain the treatment assignment information from the IWRS. Every effort is to be made to limit trial site personnel unblinding only to those individuals providing direct care to that patient. Any intentional or unintentional breaking of the blind is to be reported immediately to the sponsor.

If the blind is broken, the date, time, and reason must be recorded in the patient's eCRF, and any associated SAE report, if applicable.

2.8. ADMINISTRATION OF TRIAL MEDICATION

All 3 treatment arms involve twice-weekly dosing (glepaglutide and/or placebo) to maintain the blind. The first dose is taken on Day 1 and the second dose should be taken on either Day 4 or Day 5 of each treatment week (interval chosen at the randomization visit and adhered to throughout the trial period). Please see Table 2 for a schematic overview.

Table 2 Dosing Regimen

Second Dosing 3 Days after Visit 1								
Day	1	4	8	11	15	18	22	
Dispensing unit	ng unit 1			1 2 3		3	4	
Twice weekly DB treatment	Vial 1	Vial 2	Vial 1	Vial 2	Vial 1	Vial 2	Vial 1	
	Second Dosing 4 Days after Visit 1							
Day	1	5	8	12	15	19	22	
Dispensing unit		2		3	4			
Twice weekly DB treatment	Vial 1	Vial 2	Vial 1	Vial 2	Vial 1	Vial 2	Vial 1	

Abbreviations: DB=double-blind

2.9. SCHEDULE OF ASSESSMENTS AND PROCEDURES

For the schedule of assessments and procedures, please refer to Section 11 of this SAP, or to the latest protocol version.

3. ENDPOINTS

3.1. PRIMARY EFFICACY ENDPOINT

The primary efficacy endpoint is the change in actual weekly PS volume from baseline to Week 24.

Baseline actual weekly PS volume is defined as the actual PS volume derived from a valid 7-day period prior to Visit 1 (Day 1), i.e. during the stabilization phase. The actual weekly PS volume at Weeks 1, 2, 4, 8, 12, 16, 20, and 24 will be derived as the actual weekly PS volume received during the valid 7-day period prior to the visit. The source for the derivation will be the PS volumes recorded by the patients in the eDiary; for details on the derivation of actual weekly PS volume see Appendix A. Supportive analyses will be performed to explore the robustness of the primary analysis with regard to the algorithm for deriving the primary endpoint, see 3.1.4.

Following the treatment policy strategy, for patients who prematurely discontinue treatment but complete the trial providing eDiary information up-to Week 24, the actual weekly PS volume derived at Week 24 after treatment discontinuation will be included in the primary analysis of the primary efficacy endpoint. For patients who prematurely discontinue treatment and did not complete the trial, having an end of treatment visit (Visit 10) prior to Week 24 - 14 days (169-14 days), the derived actual weekly PS volume at the end of treatment visit will not be carried forward to represent Week 24. Instead 1) the value at Week 24 will be set to missing and imputed with the multiple imputation method described below for the primary analysis of the primary endpoint and 2) the derived actual weekly PS volume at the end of treatment visit will be re-allocated to a previous visit and used in the MMRM model. If, when re-allocating the end of treatment visit there is already a visit in the same time window, then the value of the scheduled visit will be used in the analysis, not the re-allocated end of treatment value.

The primary analysis uses a restricted maximum likelihood (REML)–based repeated-measures approach to compare treatment groups with respect to the mean change from baseline in actual weekly PS volume at Week 24. The model will use actual weekly PS volume assessments at Weeks 1, 2, 4, 8, 12, 16, 20, and 24 as an independent variable, and will include the covariates of treatment group, baseline actual weekly PS volume, visit (categorical variable), stratification factor (weekly PS volume requirements <12 L/week versus \geq 12 L/week), and visit-by-treatment group interaction. Variance estimation is based on an unstructured covariance matrix, which does not presume a particular correlation structure for repeated weekly PS volume measurements within patients over time. The primary comparisons are the contrasts (differences in least squares means) between the glepaglutide treatment groups and the placebo group at the Week 24 visit in this mixed-effects model for repeated measures (MMRM).

Missing values will be imputed using multiple imputation methods. For the primary analysis, a Copy Reference (CR) approach is used (main estimator), while for sensitivity analyses, a Jump to Reference (J2R) approach (sensitivity estimator 1) and a Copy Incremental from Reference (CIR) approach (sensitivity estimator 2) will be applied. Details are described in 5.3.1 below.

The Copy Reference approach is justified as the trophic effects on the intestines mediated by glepaglutide would take weeks to abate after treatment withdrawal. A longitudinal growth of the remaining intestines could also have occurred after prolonged therapy, and such modifications would not be expected to fully return to the baseline condition. Other effects of GLP-2 agonism-like reduced fluid secretion from the upper part of the GI tract and effects on reducing motility would, however, be expected to return to the baseline conditions when treatment is withdrawn.

As an additional sensitivity analysis (sensitivity estimator 3), the actual weekly PS volume will be derived using a valid 14-day period prior to the visit. For details on the derivation of actual weekly PS volume within a 14-day period, see Appendix A. This endpoint will be analyzed in the same manner as for the primary analysis for the primary endpoint.

Furthermore, a tipping point sensitivity analysis (sensitivity estimator 4) will be conducted to examine the impact of missing data on the primary efficacy endpoint analysis. The aim of this analysis is to explore the plausibility of missing data assumptions under which the conclusions change. The CR-imputed values will be varied independently in each treatment arm by adding an appropriate delta PS volume. The range will be determined such that it contains the tipping point, i.e. where conclusions start changing. Only clinical relevant scenarios will be included. The same primary analysis model will be applied. Conclusions from each analysis will be presented simultaneously in a heat map, with the varied delta PS volumes for imputed values in placebo treatment vs. glepaglutide TW/OW. Threshold for conclusions follow that of the testing strategy (3.3), i.e. each treatment comparison to placebo are evaluated in parallel at a two-sided 2.5% significance level. However one of the comparison may be evaluated at a two-sided 5% significance level instead, in case of alpha-recycling.

Lastly, a sensitivity analysis on the primary efficacy endpoint analysis (sensitivity estimator 5) will be conducted to examine the impact of using multiple imputation methods on missing data. This sensitivity analysis will apply the same primary analysis model on observed data only, regardless of treatment discontinuation.

A supplementary estimand will be included using a 'hypothetical strategy'. This will evaluate the difference between mean change from baseline in actual weekly PS volume at 24 weeks in the SBS population assuming that the intercurrent event of treatment discontinuation would not have occurred (i.e. patients adhere to the randomized treatment until completion). Actual weekly PS volumes derived for visits prior to treatment discontinuation will be analyzed with an MMRM model like the one described for the primary analysis of the primary endpoint.

To get an overview of the different estimands and estimators for the primary efficacy endpoint, and how missing data will be handled, please see Table 3.

Statistical Analysis Plan v6.0

Intercurrent event	Data observed or missing			Supplementary estimand 'Hypothetical'				
		Main estimator	Sensitivity estimator 1	Sensitivity estimator 2	Sensitivity estimator 3 – PS vol derived based on 14-day period	Sensitivity estimator 4	Sensitivity estimator 5	Main estimator
Prematurely discontinuation of IMP	Observed	Value used as observed	Value used as observed	Value used as observed	Value used as observed	Value used as observed	Value used as observed	Values after treatment discontinuation treated as missing
	Missing	MI (CR Placebo)	MI (J2R Placebo)	MI (CIR Placebo)	MI (CR Placebo)	MI (CR Placebo) – tipping point	Missing	Missing
No prematurely discontinuation of IMP	Observed	Value used as observed	Value used as observed	Value used as observed	Value used as observed	Value used as observed	Value used as observed	Value used as observed
	Missing	MI (CR Placebo)	MI (J2R Placebo)	MI (CIR Placebo)	MI (CR Placebo)	MI (CR Placebo) – tipping point	Missing	Missing

Abbreviations: MI = multiple imputation, CR = copy reference, J2R = jump to reference, CIR = copy increments from reference

For subjects with missing PS volume at baseline: For analyses using multiple imputation, baseline will be imputed from a model using data from patients in FAS (not only patients on placebo). For other analyses, baseline will be derived from the mean of observed baseline data from patients in FAS.

3.1.1. Clinical meaningfulness

For all treatment groups combined, the empirical cumulative distribution function (eCDF) of the percent change in actual weekly PS volume from baseline to Week 12 and to Week 24 will be plotted. The eCDF will present the cumulative proportion of patients who achieved a PS volume percent change from baseline to Week 12 and to Week 24 at each observed change level or lower.

For the 7-point scaled patient reported outcome PGIC questionnaire, the eCDF and probability density function (PDF) curves will be produced for each response category ('Very much improved', 'Much improved', 'Minimally improved', 'No change', 'Minimally worse', 'Much worse' and 'Very much worse') and presented together (in separate figures at Week 12 and at Week 24). In addition, to improve interpretability of the analysis, the PGIC categories containing very few patients will be collapsed, resulting in a three-category version as well ('Very much improved', 'Minimally improved' and 'No change'+'Minimally worse'+'Very much worse'). Figures with both the un-collapsed and collapsed categories will be presented.

In addition, the PDF of the percent reduction in the weekly PS volume from baseline to Week 12 and to Week 24 will be plotted for all treatment groups combined. The PDFs will be made for all data and by PGIC response category (and collapsed PGIC categories) and approximated using kernel density estimation and overlaid onto one graph by week, as applicable.

The correlation between PGIC and percent change in PS volume from baseline will be evaluated graphically, and by Spearman rank-order and Kendall's tau-b correlation coefficients after 12 and 24 weeks of treatment.

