9. CHANGES FROM PREVIOUS SAPS

SAP version	SAP section	Summary of change	Rationale for change
$5.0 \rightarrow 6.0$	General	• Editorial changes throughout e.g. document version, dates, table and figure references, addition/removal of sections, changes to header titles etc.	• To have a coherent document
$5.0 \rightarrow 6.0$	1.1	Responsibility of TFL generation transferred to Zealand Pharma	• To reflect internal strategic decision
$5.0 \rightarrow 6.0$	2.3	Editorial changes	• To make the specification of primary estimand of primary endpoint clear
		• Addition of supplementary estimand	• To make the specification of supplementary estimand of primary endpoint clear
$5.0 \rightarrow 6.0$	3.1	• Introduction of terminology main estimator and sensitivity estimators	• For ease of reference
		 Addition two sensitivity analyses Tipping point analysis Analysis on all observed data 	• To further explore robustness of primary analysis of primary endpoint in terms of missing data assumptions under which the conclusions change and impact of using multiple imputation methods, respectively
		• Addition of Table 3	• To provide a better overview of the various estimands and estimators, and how missing data is handled
		• Addition of Week 1 to the primary analysis model	• To accurately determine the study drug's treatment effect in the early weeks
$5.0 \rightarrow 6.0$	3.1.1	• New section divider added	• For ease of navigation
		• Definition of collapsing PGIC groups redefined	• Collapsing of groups is now made based on current data distribution to

SAP version	SAP section	Summary of change	Rationale for change
		• Spearman rank-order and Kendall's tau-b correlation coefficients added	 support interpretation in the best possible way To further specify the type of correlation coefficients used. The coefficients are chosen based on their typical use in psychometric evaluation of assessment tools
$5.0 \rightarrow 6.0$	3.1.2	New section divider added	For ease of navigation
$5.0 \rightarrow 6.0$	3.1.3	New section divider added	• For ease of navigation
$5.0 \rightarrow 6.0$	3.1.4	• New section introduced with addition of supportive analyses for primary endpoint derivation (actual weekly PS volume)	• To explore robustness of the primary statistical analysis with regard to the primary endpoint derivation

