$5.0 \rightarrow 6.0$	3.2	• Primary and supplementary estimand has been defined for each key secondary efficacy endpoint	• To further clarify the clinical question of interest and have a precise description of the treatment difference estimated for each of the key secondary efficacy endpoints
		• Primary and sensitivity analysis for primary estimand, and primary analysis for supplementary estimand are now defined for each key secondary efficacy endpoint	• To avoid any misalignment with assessment of robustness of primary estimate for each of the key secondary efficacy endpoints
		• Addition of Table 6	• To provide a better overview of the various estimands and estimators, and how missing data is handled
25 August 20		• For binary key secondary efficacy endpoints, the method for weighing and estimating CIs and type of test have been specified, along with a model Confidential	• The exact model specifications are needed before unblinding as these are confirmatory endpoints Page 52 of 65

SAP version	SAP section	Summary of change	Rationale for change
		simplication procedure in case of zero strata occurrence	
		• For binary key secondary efficacy endpoints, Wilson- Hilferty transformation has been specified for the sensitivity analysis (using CR-imputed values)	• To handle asymptotics of Cochran- Mantel-Haenszel test under the null hypothesis of no association and applying Rubin's rule
$5.0 \rightarrow 6.0$	3.3	• New high-resolution figure added	• Text in figure was not readable before
$5.0 \rightarrow 6.0$	3.4	• Addition of endpoint 'Reduction of at least 30% in actual weekly PS volume from baseline to both Weeks 20 and 24'	• To further explore different definitions for clinical response based on the outcome of the clinical meaningfulness analysis specified in 3.1.1
		• Addition of endpoint 'Reduction in prescribed weekly PS volume of 100% (weaned off) at Week 24'	• The endpoint is considered clinically relevant and thus should be prespecified
$5.0 \rightarrow 6.0$	5.3	Algorithm updated	• To align with Appendix A
5.0 → 6.0	5.3.1	Removal of tuning and thinning specifications for non-monotone MCMC procedures	• The impact of specifying these technical details in terms of convergence of the MCMC method is considered negligible, and hence not considered for the programming. Imputations of non-monotone missing data pattern will be performed using the MCMC statement in PROC MI

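### The collapsed three-category PGIC grouping in SAP 3.1.1 assigns only five of the seven responses, so *Much improved* and *Much worse* have no place in the collapsed figures

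*SAP*

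**What the plan says.** SAP 3.1.1 (Clinical meaningfulness) plans curves for each PGIC response and lists the full scale: "Very much improved', 'Much improved', 'Minimally improved', 'No change', 'Minimally worse', 'Much worse' and 'Very much worse". It then says that "the PGIC categories containing very few patients will be collapsed". The outcome is a second version with three groups: *Very much improved* on its own, followed by "Minimally improved' and 'No change'+'Minimally worse'+'Very much worse". Both displays are planned: "Figures with both the un-collapsed and collapsed categories will be presented". The grouping carries over to the density plots: "The PDFs will be made for all data and by PGIC response category (and collapsed PGIC categories".

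Three other places bear on it:

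- **SAP 3.4** defines PGIC improvement as either of the top two responses. It also has its own three-level grouping (improvement, no change, worsening) for a separate test.
- **SAP 5.3.2** mentions curves by collapsed response category but does not define the categories.
- **SAP 9** records that the 3.1.1 grouping was redefined in version 6.0: "Collapsing of groups is now made based on current data distribution". It also explains the added 30% response endpoint as exploring other definitions of response "based on the outcome of the clinical meaningfulness analysis specified in 3.1.1".

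**The concern.** A grouping of an ordinal scale should give every response one place. This one leaves two responses without any. The text calls the operation collapsing, which means merging, yet on the improvement side nothing is merged: the first and third responses stand alone and the one between them is missing. On the other side, the bottom group joins *Minimally worse* to *Very much worse* and skips the response between them.

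The collapsed curves exist because some of the seven categories may be too thin to read. They are therefore likely to be used when judging what size of PS reduction patients notice. An anchor display without *Much improved* does not correspond to the responder definition in SAP 3.4.

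Quality control may not catch it. SAP 12 relies on two programmers working independently to the same specifications. If both follow this line literally, both omit the same patients and the comparison shows no difference. If both guess, they may guess differently.

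**Working it through.** No sample-size, power or alpha formula applies, and the plan states no figure to reproduce. The check sets the label lists side by side.

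**Inputs.** The seven-label list and the collapsed list are from SAP 3.1.1. The responder definition and the three-level grouping are from SAP 3.4.

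| Response | 3.1.1 collapsed group | 3.4 responder | 3.4 three-level grouping |
|---|---|---|---|
| Very much improved | group 1 | yes | improvement |
| Much improved | **none** | yes | improvement |
| Minimally improved | group 2 | no | improvement |
| No change | group 3 | no | no change |
| Minimally worse | group 3 | no | worsening |
| Much worse | **none** | no | worsening |
| Very much worse | group 3 | no | worsening |

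**Counts.**

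- 3.1.1 collapse: 1 + 1 + 3 = 5 labels assigned; 7 − 5 = 2 unassigned.
- 3.4 three-level grouping: 3 + 1 + 3 = 7 labels assigned; 0 unassigned.
- 3.4 responder labels missing from the 3.1.1 collapse: 1 of 2 (*Much improved*).

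**Is the gap filled elsewhere?** No. SAP 5.3.2 refers to the collapsed categories without a mapping. SAP 9 says the mapping was changed in light of the data but does not give one. The SAP 3.4 grouping covers all seven labels, but it belongs to a different analysis and cuts the scale differently.

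**Which outputs are touched?**

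- Affected: the eCDF and density figures by collapsed category, at Weeks 12 and 24.
- Not affected: the overall eCDF, the seven-category curves, the density for all data, the Spearman and Kendall coefficients, the PGIC tests in 3.4, and the primary and key secondary tests under 3.3.

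**What happens to the collapsed curves that remain?** Each curve is drawn only from the patients in its own group. The *Very much improved* and *Minimally improved* curves are therefore the same whether or not *Much improved* is shown separately. The bottom curve would change only if *Much worse* belongs there and some patients gave that response.

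**The case against.** The strongest case on the other side is that this is a slip in one line of a descriptive figure. The governing word is collapsed, the skipped *Much worse* suggests that two labels fell out of the line, and an attentive programmer or the senior statistician would query two unassigned codes. The seven-category figures are shown as well. All of that is plausible, and it is why the point is a small one. It does not remove the need for correction, since a pre-specified grouping should not depend on someone guessing the missing labels.

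A second defence is that the two categories were empty in the data seen when version 6.0 was written. The SAP does not say so. Version 6.0 is dated 25 August 2022 and the protocol synopsis estimates last patient completion in Q3 2022, so the distribution may not have been final. Even for an empty category, the rule should say where a response would go.

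Three stronger readings are tempting, and the documents do not support them:

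- **A reader might infer that the apparent threshold for a meaningful PS reduction shifts.** The two improvement curves in the collapsed display do not move, as shown above, and 3.1.1 gives no rule for reading a threshold from the collapsed figure. What is lost is an intermediate group.
- **A reader might infer that a sizeable share of the roughly 108 patients is lost.** Any such count needs a PGIC distribution that neither document gives.
- **A reader might infer that the 30% response endpoint rests on a faulty display.** SAP 9 cites the 3.1.1 analysis as a whole, most of which keeps these patients. The endpoint is already written into 3.4 and is tested without multiplicity adjustment.

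**Conclusion.** The concern holds in a limited form. The collapsed PGIC grouping in SAP 3.1.1 is incomplete: 2 of 7 responses are unassigned, including 1 of the 2 that SAP 3.4 counts as improvement. Taken literally, patients giving those responses are missing from the collapsed eCDF and density figures at both visits. Their number is unknown, and would be zero if nobody gave either response.

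The consequence stays within a descriptive display pooled over treatment groups. No confirmatory test, estimand, alpha allocation or sample size depends on it. The conclusion assumes that the printed line is the intended specification and that no separate programming document supplies the missing mapping. It is still worth correcting, because the display is part of the analysis that the SAP cites when exploring response definitions.

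**What to change.** Before unblinding, restate the collapse in SAP 3.1.1 so that each of the seven responses belongs to exactly one group, and point to the same mapping from 5.3.2. One version that agrees with the responder definition in 3.4 is:

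- *Very much improved* + *Much improved*
- *Minimally improved*
- *No change* + *Minimally worse* + *Much worse* + *Very much worse*

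This assigns 2 + 1 + 4 = 7 labels. It is an example, not the only reading: 3.4 also has a grouping that puts all three improved responses together, and SAP 9 says the collapse follows the data distribution. The sponsor should confirm the group intended for *Much improved* and add a sentence explaining why the 3.1.1 and 3.4 groupings differ, if they do.

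The cost is one line of SAP text and the matching program specification. Fixing the mapping before unblinding also avoids any suggestion that the anchor groups were chosen with the results in view.
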